#### SECONDARY OBJECTIVES:

Key Secondary objectives:

- To assess the efficacy of ADT + darolutamide vs ADT + placebo in terms of:
  - Castration-resistant prostate cancer-free survival
  - Clinical progression-free survival (cPFS)
  - Overall survival
- To assess the safety profile of the ADT + darolutamide combination.

Other secondary objectives:

- Time to worsening in prostate cancer-related urinary symptoms
- Time to next symptomatic skeletal event
- Prostate specific antigen (PSA) response
- Prostate cancer-specific survival
- To assess the effect of ADT + darolutamide on subsequent lines of therapy
- To evaluate the evolution of quality of life and geriatric status in individuals during the treatment period.
- To evaluate the impact of sarcopenia on survival and treatment response.

**EXPLORATORY OBJECTIVES**

- To identify the oncogenic drivers of *de novo* metastatic prostate cancer.

**DIAGNOSIS AND INCLUSION CRITERIA:**

To be eligible, patients must meet all of the following criteria:

1. Signed a written informed consent form prior to any trial specific procedures.  
**Note:** *If the patient is physically unable to provide their written consent, a trusted person of their choice, independent of the Investigator or the Sponsor, can confirm the patients consent in writing.*
2. Men with histologically or cytologically confirmed adenocarcinoma of the prostate.
3. Aged  $\geq 18$  years old at the time of signing informed consent.
4. *De novo* metastatic disease defined by clinical or radiographic evidence of metastases.  
**Note:** *For patients with nodal metastases only, only patients with extra-pelvic enlarged lymph nodes (lymph nodes located above the iliac bifurcation) can be included if they have either:*
  - *At least one extra-pelvic lymph node  $\geq 2$  cm*
  - *At least one extra-pelvic lymph node  $\geq 1$  cm if the patients also have at least one pelvic lymph node  $\geq 2$  cm*
5. Measurable disease or bone lesions that are evaluable according to PCWG3 criteria.
6. Ineligible for treatment with all of the following drugs: docetaxel, abiraterone, enzalutamide, apalutamide; AND meets at least one of the following frailty criteria:
  - a. Activities of daily living (ADL) assessment (excluding urinary incontinence question) score 3 or 4/5, or;
  - b. 4-Instrumental activities of daily living (4-IADL) assessment score 2 or 3/4, or;
  - c. A Grade 3 event on the Cumulative Illness Score Rating-Geriatrics (CISR-G) questionnaire, or;
  - d. Body mass index (BMI)  $\leq 21$  kg/m^2 and/or  $>5\%$  weight loss in the last 6 months, or;
  - e. Timed up and go test (TUG)  $>14$  sec.

*Nota Bene: Regarding CISR-G assessment, more specifically genitourinary scoring, score N°4 is not applicable*

7. Adequate bone marrow function: haemoglobin  $\geq 80$  g/L, white blood cells  $\geq 3.0 \times 10^9$ /L and platelets  $\geq 80 \times 10^9$ /L.
8. Adequate liver function: alanine aminotransferase (ALT)  $< 2 \times$  upper limit of normal (ULN) and bilirubin  $< 1.5 \times$  ULN, (or if bilirubin is between  $1.5-2 \times$  ULN, they must have a normal conjugated bilirubin). For patients with documented liver metastasis, ALT  $< 5 \times$  ULN is acceptable.
9. Adequate renal function: calculated creatinine clearance  $> 30$  ml/min (using the MDRD or CKD EPI method).
10. For sexually active men, agreement to use adequate contraception for the duration of trial participation and up to 2 weeks after completing study treatment.
11. Affiliated to the social security system or in possession of equivalent private health insurance (according to local regulations for participation in clinical trials).
12. Willing and able to comply with the protocol for the duration of the trial including undergoing treatment and scheduled visits, and examinations including follow-up.

#### NON-INCLUSION CRITERIA:

Patients are not eligible to participate in the trial if they meet any of the following criteria:

1. Three or more Grade 3, or any Grade 4 events on the CISR-G questionnaire  
*Nota Bene: (Regarding CISR-G assessment, more specifically genitourinary scoring, score N°4 is not applicable).*
2. Eastern Cooperative Oncology Group (ECOG) performance status score  $\geq 3$ .
3. Hypertension not controlled by an anti-hypertensive treatment (systolic blood pressure [BP]  $\geq 160$  mmHg or diastolic BP  $\geq 95$  mmHg; 3 consecutive measures taken 5 minutes apart).
4. Acute toxicities of prior treatments and procedures not resolved to grade  $\leq 1$  or baseline before randomisation, with the exception of hot flushes and erectile dysfunction.
5. Previous systemic treatment for prostate cancer, except less than 12 weeks of ADT and/or an old-generation AR inhibitor.
6. Severe or uncontrolled concurrent disease, infection or co-morbidity.
7. Known hypersensitivity to the study treatment or any of its ingredients.
8. Major surgery within 28 days before randomisation.
9. Any of the following within 6 months before randomisation: stroke, myocardial infarction, severe/unstable angina pectoris, coronary/peripheral artery bypass graft; congestive heart failure New York Heart Association (NYHA) Class III or IV.
10. Prior malignancy  $\leq 3$  years before study enrolment. Adequately treated basal cell or squamous cell carcinoma of skin or superficial bladder cancer that has not spread behind the connective tissue layer (i.e., pTis, pTa, and pT1) is allowed, as well as any localized

cancer for which treatment has been completed  $\geq 6$  months before randomisation and from which the subject has been disease-free, or for which the risk of relapse is less than 30%, as well as early stage chronic lymphocytic leukaemia that does not require any specific treatment.

11. Inability to swallow oral medications.
12. Gastrointestinal disorder or procedure that can be expected to interfere significantly with the absorption of study treatment.
13. Known to have active viral hepatitis, active human immunodeficiency virus (HIV) or chronic liver disease at screening.
14. Treatment with any investigational product within 28 days before randomisation.
15. Concurrent participation in another clinical trial involving an investigational product (patients enrolled in non-experimental trials with no modification of the standard of care can be included).
16. Individual of full age deprived of liberty or placed under a legal protection measure (tutorship/curatorship/temporary guardianship).
17. Significantly altered mental status prohibiting the understanding of the study or with psychological, familial, sociological or geographical condition potentially hampering compliance with the study protocol and follow-up schedule or any condition that, in the opinion of the investigator, would preclude participation in this trial.

#### PRIMARY ENDPOINT:

Radiographic progression-free survival, defined as time from randomisation to radiographic progression as assessed by the investigator according to PCWG3 criteria, or death, whichever occurs first.

*According to the PCWG3 recommendations, radiographic progression is defined as either the appearance of two or more new bone lesions on bone scan or a nodal or visceral progression according to Response Evaluation Criteria in Solid Tumours version 1.1 (RECIST v1.1). The date of radiographic progression will be the date of the first reported event meeting the above definition.*

#### SECONDARY ENDPOINT(S):

##### Key secondary endpoints:

- Castration-resistant prostate cancer (CRPC)-free survival, defined as the time from randomisation to onset of CRPC according to PCWG3 criteria, or death, whichever occurs first.
- Clinical progression-free survival, defined as time from randomisation to first occurrence of any one of the following:
  - Cancer pain deterioration (2-point deterioration from baseline according to the Brief Pain Inventory - Short Form [BPI-SF] questionnaire, or initiation of opioid therapy, or a  $\geq 30\%$  increase in opiate use),
  - Any deterioration of physical function measured using the 4-IADL assessment tool,
  - A deterioration in ECOG performance status of at least 2 points from baseline,
  - Death from any cause.

- Overall survival, defined as the time from randomisation to the time of death from any cause. For subjects alive at the time of analysis, data will be censored on the last date the subject was known to be alive or lost to follow-up or to have withdrawn consent.
- Toxicity will be evaluated according to version 5.0 of the National Cancer Institute - Common Terminology Criteria for Adverse Events (NCI-CTCAE v5.0).

#### Other secondary endpoints:

- Time to worsening in prostate cancer-related urinary symptoms, defined as an increase from baseline of greater or equal to 8 points in the urinary symptom scale/score (PRURI), measured using the prostate cancer module of the European organisation for research and treatment of cancer (EORTC) quality of life questionnaire (QLQ) (EORTC-QLQ-PR25).
- Time to next symptomatic skeletal event, defined as the time from randomisation until first occurrence of one of the following: a symptomatic fracture, radiation or surgery to bone or a spinal cord compression (PCWG3 criteria).

**Note:** The occurrence of these events will be determined by investigator evaluation. No systematic X-Ray will be performed.

- Complete PSA response (defined as PSA  $\leq$  0.2 ng/ml) at 6 months.
- Prostate cancer-specific survival, defined as the time from randomisation to the date of death due to prostate cancer (deaths due to other causes will be censored).
- Time to deterioration for EORTC QLQ-PR25 symptom subscales, defined as the first decline in the HRQoL score from baseline equal to or greater than the minimally important difference (MID; a measure of clinical significance) defined as half the standard deviation of the baseline value for each subscale.
- Time to first subsequent systemic anti-cancer therapy (SACT) defined as the time from randomisation to the date of initiation of any SACT for CRPC, following initiation of the study treatment.
- Efficacy of subsequent SACT will be assessed according to rPFS, OS, and PFS after next line of treatment (PFS2); defined as the time from randomisation to second objective disease progression, or death from any cause, whichever first.
- Health related quality of life will be evaluated using the EORTC-QLQ-C30, EORTC-QLQ-PR25 and BPI-SF questionnaires.
- Geriatric status will be evaluated using the Geriatric Core Dataset (G-Code) assessment.
- Impact of sarcopenia on overall survival will be evaluated by comparing the distribution of overall survival between sarcopenic and non-sarcopenic patients.
- Impact of sarcopenia on treatment response will be evaluated by comparing rate of response in sarcopenic and non-sarcopenic patients.

## D) INVESTIGATIONAL MEDICINAL PRODUCTS

### PRODUCT NAMES AND ADMINISTRATION:

Drug name (INN)	Registered name 	Pharmaceutical form	Administration route	Posology
-----------------	--------------------------------	---------------------	----------------------	----------

Nubeqa	Darolutamide	300 mg tablets	oral	600 mg b.i.d
(1) When any generic drug can be is used indicate only the international nonproprietary name (INN). The choice of the registered name or brand name used in the trial is at the investigators discretion.				
THERAPEUTIC REGIMENS: 
 
Experimental arm: ADT + darolutamide 600 mg po b.i.d
 
Control arm: ADT + placebo po b.i.d.
 
 
The choice of ADT is left to the discretion of the investigator, to be administered according to local standard procedures.
				
TREATMENT DURATION: 
Treatment will be continued until radiographic disease progression. Treatment may also be terminated at the initiative of either the patient or the investigator for any reason that would be beneficial to the patient, including: unacceptable toxicity, intercurrent conditions that preclude continuation of treatment, or patient request.
				

## DOSE MODIFICATION:

### **General requirements for dose modifications**

A patient who experiences a Grade 3 or 4 AE that is considered related to the study drug (darolutamide/placebo), should interrupt the study drug until the AE improves to Grade  $\leq 2$  or to baseline status. More specific guidance on how to proceed in the case of Grade 3-4 AEs is provided in the protocol in section 5.5 dose adaptation.

#### **1- Study drug dose modifications for all AEs except for increases in ALT/AST**

A patient who is experiencing a  $\leq$  Grade 2 AEs (according to NCI-CTCAE v5.0), should keep receiving treatment as per protocol schedule. It is per investigator's decision to interrupt or to reduce study drug (darolutamide/placebo).

If a patient experiences a  $\geq$  Grade 3 toxicity that is considered as related to the study drug (darolutamide/placebo):

- Treatment should be withheld until the AE improves to Grade  $\leq 2$  or to baseline status.
- When the severity is Grade  $\leq 2$ , restart at a reduced dose of 300 mg b.i.d. Re-escalation to 600 mg b.i.d may be considered by the investigator when AE returns to baseline or is resolved.
- If there is no recovery after 28 consecutive days, treatment with darolutamide/placebo should be permanently discontinued.
- If, following a re-escalation to 600 mg b.i.d, a second Grade  $\geq 3$  AE occurs, a permanent dose reduction to 300 mg b.i.d is required.
- If a 3rd occurrence of Grade  $\geq 3$  AE occurs while the participant is on a dose of 300 mg b.i.d (following temporary or permanent dose reduction), the patient must be withdrawn from study treatment.

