#### 5.5. Dose adaptation

##### **General requirements for dose modifications**

A patient who experiences a Grade 3 or 4 AE that is considered related to the study drug (darolutamide/placebo), should interrupt the study drug until the AE improves to Grade  $\leq 2$  or to baseline status. Specific guidance on how to proceed in the setting of Grade 3-4 AEs is provided in Table 1 Study drug dose modifications for all AEs except for increases in ALT/AST” and Table 2 Study drug dose modifications for increases in ALT and/or AST” .

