##### **5.5.1. Study drug dose modifications for all AEs except for increases in ALT/AST**

**Table 1 Study drug dose modifications for all AEs except for increases in ALT/AST**

Severity grade (NCI-CTCAE v5.0)	Dose modifications	Study treatment withdrawal
Grade 0 – 2	Treat on time Per investigator’s decision to interrupt or reduce study drug a,b	Not applicable
Grade 3 – 4	Interrupt until Grade $\leq 2$ or baseline a ,	If Grade $\geq 3$ study drug-related AE occurs while the participant is on a

	When the severity is Grade $\leq 2$ , restart at a reduced dose 300 mg b.i.d b,c	dose of 300 mg b.i.d (following temporary or permanent dose reduction), the participant must be withdrawn from treatment with study drug
--	---	--

Excludes clinically non-significant and asymptomatic laboratory abnormalities

AE = Adverse Event; ALT = Alanine aminotransferase; AST = Aspartate aminotransferase; b.i.d = Twice daily; NCI-CTCAE v5.0 = National Cancer Institute Common Terminology Criteria for Adverse Events version 5.0;

a: If there is no recovery after 28 consecutive days, treatment with study drug should be permanently discontinued.

b: when AE returns to baseline or is resolved, re-escalation to 600 mg b.i.d may be considered by the investigator.

c: If, following a re-escalation to 600 mg b.i.d, a second Grade  $\geq 3$  study drug-related AE occurs, a permanent dose reduction to 300 mg b.i.d is required. A third occurrence of a Grade  $\geq 3$  study drug-related AE requires permanent discontinuation of treatment with study drug.

In the event of treatment interruption due to toxicity of more than 56 days, the decision to restart treatment or not should be discussed and agreed between the Investigator and Sponsor.

Dose reduction below 300 mg b.i.d is not recommended because efficacy has not been established. The maximum efficacious daily dose is the recommended dose of 600 mg b.i.d.

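### The protocol summary makes withdrawal on 300 mg b.i.d. mandatory only at a third related Grade 3 or higher AE; section 5.5.1, Table 1 makes it mandatory at any such AE on that dose

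*Protocol*

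**What the plan says.** Two current texts govern the study drug after a related Grade 3 or higher AE other than an ALT/AST increase.

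- **Protocol summary, part D, dose modification 1.** The list is introduced as applying to "toxicity that is considered as related to the study drug (darolutamide/placebo". Treatment is withheld, and once the event has fallen to Grade 2 or lower the instruction is to "restart at a reduced dose of 300 mg b.i.d. Re-escalation to 600 mg b.i.d may be considered by the investigator". A second event after re-escalation brings a permanent reduction to 300 mg b.i.d. The last bullet opens "If a 3 rd occurrence of Grade" and continues that if this event "occurs while the participant is on a dose of 300 mg b.i.d (following temporary or permanent dose reduction), the patient must be withdrawn". The withdrawal meant is from the study drug.
- **Section 5.5.1, Table 1, study treatment withdrawal column (Grade 3–4 row).** If a related Grade 3 or higher AE occurs on a "dose of 300 mg b.i.d (following temporary or permanent dose reduction), the participant must be withdrawn from treatment with study drug". There is no occurrence count.
- **Section 5.5.1, Table 1, footnote c.** The marker sits on the restart instruction in the dose modifications column. The footnote starts from re-escalation to 600 mg b.i.d., requires permanent reduction at a second event, and ends by saying that a third Grade 3 or higher "study drug-related AE requires permanent discontinuation of treatment with study drug".

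Both places also point to a more specific text. The summary says "More specific guidance on how to proceed in the case of Grade 3-4 AEs is provided in the protocol in section 5.5", and section 5.5 says "Specific guidance on how to proceed in the setting of Grade 3-4 AEs is provided in Table 1".

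**The concern.** The summary bullet and the Table 1 withdrawal cell are nearly the same sentence. Both cover temporary and permanent reductions and both make withdrawal mandatory, but only the summary adds a count of three. The bullet appears to merge two separate rules of section 5.5.1: the cell (any event on 300 mg) and footnote c (third event, on the re-escalation path).

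This is a mandatory safety rule in patients selected for frailty, at the lowest dose the protocol recommends. A site working from Table 1 must stop the drug after a second related severe event on 300 mg b.i.d., whereas a site working from the summary may restart it. With 100 planned sites, exposure, discontinuation and protocol-deviation data could differ according to which page a site uses.

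**Working it through.** No formula applies. The check sets the two rules side by side and follows them through the possible sequences of related Grade 3 or higher AEs, by dose at onset.

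**Inputs**

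| Element | Summary, dose modification 1 | Section 5.5.1, Table 1 |
|---|---|---|
| Relatedness | Related (from the lead-in to the list) | Related (stated in the cell) |
| Dose at the event | 300 mg b.i.d., temporary or permanent reduction | 300 mg b.i.d., temporary or permanent reduction |
| Occurrence count | Third | None in the cell; third in footnote c |
| Consequence | Mandatory withdrawal | Mandatory withdrawal |

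**Main paths, no discretionary reduction.** Event 1 occurs on 600 mg b.i.d. and the patient restarts at 300 mg b.i.d. under both texts. There are then two branches.

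*Not re-escalated (600 – 300 – 300).*
- Event 2 on 300 mg. Table 1: withdraw. Summary: no withdrawal rule applies, which leaves the general bullets (withhold, then restart at 300 mg).
- Event 3 on 300 mg. Summary: withdraw.
- Mandatory withdrawal falls at event 2 under Table 1 and event 3 under the summary. Difference: 3 − 2 = 1 event.

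*Re-escalated (600 – 600 – 300).*
- Event 2 on 600 mg. Both texts: permanent reduction to 300 mg b.i.d.
- Event 3 on 300 mg. Table 1 (cell and footnote c): withdraw. Summary: withdraw.
- Mandatory withdrawal falls at event 3 under both. Difference: 3 − 3 = 0.

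The texts therefore conflict in one of the two branches, by one event.

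**The word temporary in the summary bullet.** In the re-escalated branch the reduction in force at event 3 is permanent. Discretionary reductions aside, a third event on a temporary reduction can arise only in the other branch, and only if event 2 on 300 mg did not end treatment. Taken literally, the bullet presupposes continuation where Table 1 requires withdrawal.

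**Discretionary reduction, kept separate.** Both texts let the investigator reduce the dose for a Grade 2 or lower AE. If the first related Grade 3 or higher AE then occurs on 300 mg b.i.d., Table 1 read literally requires withdrawal at event 1. The summary, if the patient stays on 300 mg, requires it only at event 3. Difference: 3 − 1 = 2 events. The protocol does not say whether the rule was meant to reach this case, so it is left out of the main count.

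**The case against.** The strongest objection concerns which text is wrong. The closing sentence of footnote c does not itself mention re-escalation. Read on its own it is a general third-occurrence rule resembling the summary, and no clause says which text prevails. This does not remove the conflict. Even as a general rule, the sentence is a second sufficient condition for stopping: it requires discontinuation at a third event and does not permit continuation at a second event on 300 mg. The cell and the footnote can both be obeyed, so section 5.5.1 is consistent with itself and the summary is the outlier. The pointers to section 5.5 and Table 1 support the same reading.

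Two further objections stand in part. Temporary may simply have been carried over from the cell when the bullet was drafted, so it shows what the bullet says but not what the sponsor intended. And restarting at 300 mg after a second event on 300 mg is an inference: the restart bullet describes a reduced dose, which fits a patient coming down from 600 mg, and the summary gives no express instruction for a second event on 300 mg. A site that follows the cross-reference reaches the Table 1 rule. But the summary is a complete directive list that can be applied without consulting section 5.5, and its count of three implies continuation after the second event.

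Practical weight is also limited. The main branch needs two related severe events outside the ALT/AST rules and no re-escalation. Table 1 excludes clinically non-significant asymptomatic laboratory abnormalities. The investigator may stop for unacceptable toxicity at any time, so the summary permits continuation without forcing it.

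**Conclusion.** The concern holds. For the same patient the two texts set different mandatory withdrawal points: event 2 under Table 1 and event 3 under the summary when the patient has not been re-escalated, and event 3 under both when he has. This count assumes no discretionary reduction for a lower-grade AE; with one, the literal gap can be two events.

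That the summary is the text to correct rests on the internal consistency of section 5.5.1 and on the cross-references to it, since no precedence clause exists. How many patients are affected cannot be derived from the protocol. The consequence is for patient safety and for exposure, discontinuation and deviation data; the ITT primary analysis and its type I error are unaffected. The correction should be made, but the matter does not threaten the trial's main conclusion.

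**What to change.** Replace the last bullet of the summary's dose modification 1 with the Table 1 rule: any study drug-related AE of Grade 3 or higher that arises on 300 mg b.i.d., whether the reduction was temporary or permanent, ends study drug treatment. Keep the footnote c rule as a separate bullet limited to patients re-escalated to 600 mg b.i.d.: permanent reduction at the second event, discontinuation at the third.

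The sponsor should also decide whether the rule covers a first related Grade 3 or higher AE on 300 mg b.i.d. after a discretionary reduction for a Grade 2 or lower AE, and state the answer in the same words in the summary and in Table 1.

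The cost is one wording change at the next amendment and a short letter to sites, with no new procedures or data. At the current amendment about 115 of 300 patients were enrolled, so 300 − 115 = about 185 were still to enter and could be managed under a single rule.
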